## **5.2 Per-protocol Set**

The Per-protocol Set (PPS) will include all patients in the mITT Population who did not have a major protocol deviation, as defined in a separate document, Protocol Deviation Plan. Major protocol deviations for the PPS will be determined prior to unblinding of the study data.

This population will be used in a supplementary analysis for the primary endpoint.

## **5.3 Safety Analysis Population**

The Safety Analysis Population will include all randomized patients who received at least 1 dose of the study treatment. The population will be analyzed according to the treatment that patients actually received, rather than the study treatment to which patients were randomized.

This population will be used in all safety analyses.

## **5.4 Pharmacokinetic Concentration Population**

The Pharmacokinetic Concentration (PK-C) Population will include all patients who received at least 1 dose of naldemedine and had at least 1 evaluable concentration of either naldemedine or nor-naldemedine in plasma. This population will be used for the concentration listing.

## **5.5 Pharmacokinetic Parameter Population**

The Pharmacokinetic Parameter (PK-P) Population will include all patients with at least 1 PK parameter estimated appropriately. This population will be used for PK parameter listings and summaries, plotting of the plasma concentration-time data, plasma concentration summaries, and statistical analysis.

# **6. STATISTICAL CONSIDERATIONS FOR DATA ANALYSES AND HANDLING**

## **6.1 Statistical Reporting**

Unless otherwise noted, continuous variables will be summarized by using the number of nonmissing observations, arithmetic mean, standard deviation (SD), median, and minimum, and maximum values as summary statistics; categorical variables will be summarized by using the frequency count and the percentage of patients in each category.

Patient study data, including data not appearing in tables, will be presented in by-patient data listings. In general, all tables will be presented by treatment group. Individual patient data and any derived data will be presented by treatment and patient.

All analyses will be performed using SAS® Version 9.4 or higher (SAS Institute, Cary, NC, USA), or WinNonlin Version 6.2.1 or higher (Certara, St Louis, MO, USA).

## 6.2 Statistical Testing

All statistical tests will be performed at the 2-sided significance level of 0.05, unless otherwise noted. No multiplicity adjustment will be made in this study.

## 6.3 Analysis Visit Windows

No analysis visit window will be applied. The data will be collected according to Figure 1-2 and Table 1-2 in the protocol and analyzed according to the time point collected on the case report form (CRF).

## 6.4 Missing Data

Missing values will not be imputed. All statistical analyses will be based on observed cases unless otherwise noted.

## 6.5 Definition

### 6.5.1 Study Day

For programming and analysis purposes, the study days specified in the protocol will be mapped as shown in Table 1. Study day will be presented in this SAP in the same way as presented in the protocol, while TLF shells and TLFs will present “Surgery Day” or “Postop Day X” as shown in parentheses in this mapping table.

**Table 1** Mapping Information for Study Days

Protocol Day	Screening Period	Treatment Period									Follow-up Period
		Day 0		Day 1	Day 2	Day 3	Day 4	Days 5 to 10	Day of Discharge	Early Termination	
	Baseline	Before Surgery	After Surgery								
Mapped Analysis Day	Day -14 to 1	Day 1 Before Surgery (surgery day)	Day 1 After Surgery (surgery day)	Day 2 (Postop Day 1)	Day 3 (Postop Day 2)	Day 4 (Postop Day 3)	Day 5 (Postop Day 4)	Days 6 to 11 (Postop Days 5 to 10)	Day of Discharge	Early Termination	End-of-study Visit

Postop = postoperative

Study Day 0 will be the day of surgery, and any other study day will be calculated relative to Study Day 0. Therefore, Day 1 will start at midnight after surgery of that calendar day and Day X (X = 1, 2, .., 10) will start at midnight of the X-th day. “Study Day” will simply be represented as “Day” hereafter in this SAP.

### 6.5.2 Baseline

Baseline except for the Numerical Pain Rating Scale (NPRS) will be defined as the last value obtained before randomization. The baseline value for NPRS will be the value as assessed on the morning of Day 1.

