Exploratory	
 To compare the efficacy of naldemedine 1.25 mg, 2.5 mg, and 5 mg and placebo for the exploratory endpoints Time from the end of surgery to time to discharge readiness Time from the end of surgery to time of actual discharge (departure) from the hospital Proportion of patients with prolonged hospital stay due to gastrointestinal dysfunction Time from initial insertion of the nasogastric tube to removal of the nasogastric tube Proportion of patients with abdominal distention on Day 1 through the day on which GI2 is achieved Proportion of patients with nausea on Day 4 through day of discharge Proportion of patients with vomiting on Day 4 through day of discharge Proportion of patients who achieve GI2 in each treatment group by postoperative day Proportion of patients who receive concomitant medication that may have a laxative effect Effect of prior surgery (yes/no) on the GI2 endpoint
Pharmacokinetics	
 To characterize the pharmacokinetics (PK) profile of naldemedine 1.25 mg, 2.5 mg, and 5 mg and its metabolite (nor-naldemedine) for the PK endpoints Plasma drug concentrations of naldemedine and nor-naldemedine on: 
 Day 2 immediately before the morning dose Day 3 immediately before the morning dose and 1 hour and 2, 4, 8, and 12 hours after the morning dose before administration of the evening dose Day 4 immediately before the morning dose PK parameters of naldemedine and nor-naldemedine (C_{max}, T_{max}, AUC, CL/F, $MR_{M/U}$, C_{max}, and $MR_{M/U}$, AUC)
Safety	
 To compare the safety of naldemedine 1.25 mg, 2.5 mg, and 5 mg and placebo for the safety endpoints Incidence of treatment-emergent adverse events, including those that are serious and those that result in discontinuation of study treatment

	
• Proportion of patients with clinically significant changes in clinical laboratory tests, vital signs, and ECGs• Change from baseline in pain intensity, as assessed on a Numerical Pain Rating Scale (NPRS)• Total dose of intra- and postoperative opioid analgesics in morphine milligram equivalents (MMEs)
--	--

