- j To be measured once daily as close as possible after waking; vital signs include systolic/diastolic blood pressure (assessed after approximately 3 to 5 minutes of rest), and pulse rate.
- k To be performed any time from 14 days to day of surgery (Day -14 to Day 0, respectively). An electrocardiogram obtained within 2 weeks prior to the patient signing the informed consent form that shows no clinically significant abnormal finding may be used.
- l To be assessed once daily in the morning at approximately the same time of day; baseline is defined as the pain assessment on the morning of Day 1.
- m Hematology (platelet count, erythrocytes [red blood cell count], hemoglobin, hematocrit, leukocytes [white blood cell count with differential: neutrophil count, lymphocyte count, monocyte count, eosinophil count, basophil count]), clinical chemistry (blood urea nitrogen, creatinine, chloride, potassium, sodium, calcium, aspartate aminotransferase, alanine aminotransferase, alkaline phosphatase, total bilirubin, international normalized ratio, total protein, and albumin).
- n Required for female patients of childbearing potential (that is, not surgically sterile by hysterectomy, bilateral oophorectomy, and/or bilateral salpingectomy or tubal ligation with appropriate documentation of such surgery *OR* not postmenopausal [defined as at least 12 months of spontaneous amenorrhea in a woman > 45 years of age]). If the urine pregnancy test is obtained prior to Day -1 and is negative, the test must be repeated on Day -1 or Day 0. Additional pregnancy testing is not required during the treatment period unless clinically indicated.
- o The actual date and time (24-hour clock) of all study treatment dosing and each meal prior to dosing will be recorded in the eCRF.
- p First dose is to be administered 30 minutes to 6 hours prior to the scheduled start of surgery on the operative day (Day 0).

- q A second dose will be administered postoperatively the evening of the operative day (Day 0).

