- r Beginning on Day 1, patients will receive study treatment BID for up to 10 days postoperatively (ie, Day 10). Every effort will be made to give all morning and evening doses at approximately 12-hour intervals. The duration of study treatment will be determined by the date on which the primary endpoint, GI2 (patient tolerates solid food and has a bowel movement), is met or the date on which the discharge order is written, whichever occurs first, and will not exceed 10 postoperative days. Study treatment may be administered on the day of discharge.
- s Any overdose or medication error of the study treatment must be reported to the contract research organization's medical monitor via eCRF (or paper form if EDC is not available) by the investigator or qualified designee using a Special Situations Report Form as soon as becoming aware.
- t To be assessed until both time to first toleration of solid food (defined as the time when the patient consumes a meal that requires chewing and has no significant nausea or vomiting, as per the judgment of the investigator, for 4 hours after that solid food) and first bowel movement occur and to be recorded in the eCRF. If a patient is discharged from the hospital prior to having a first bowel movement, he/she is to be instructed to inform the investigator or qualified designee by phone within 24 hours of having a first bowel movement up to and including Day 10. Additionally, the investigator or qualified designee will communicate (phone, text, or e-mail) with the patient daily up to and including Day 10 to record when the first bowel movement occurred.
- u Discharge readiness is defined as gastrointestinal recovery based on the clinical judgment of the investigator (yes or no).

Table 1-2 Schedule for Pharmacokinetic Sample Collection

Day	Time					
	Predose	Postdose (hour)				
		0	1	2	4	8
2	X ^{a, b}					
3	X ^{a, b}	X ^{b, c}				
4	X ^{a, b}					

a Immediately before the morning dose.

b Required only if the patient remains hospitalized.

c Performed after the morning dose but before administration of the evening dose.

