The first dose of study treatment will be administered 30 minutes to 6 hours prior to the scheduled start of surgery on the operative day (Day 0), and the second dose will be administered postoperatively the evening of the operative day. Beginning on Day 1, patients will receive study treatment BID for up to 10 days postoperatively (ie, Day 10). Every effort will be made to give the Day 1 morning dose approximately 12 hours after the Day 0 evening dose and to give all morning and evening doses from Days 1 to 10 at approximately 12-hour intervals. Note that duration of administration will be determined by the date on which the primary endpoint, GI2, is met or the date on which the discharge order is written, whichever occurs first, and will not exceed 10 postoperative days (excluding the postoperative dose on Day 0). Study treatment may be administered on the day of discharge. Details regarding study treatment administration are provided in [Section 6.1](#).

During the treatment period, procedures and assessments will be performed as specified in the Schedule of Activities (SoA) in [Section 1.3](#).

Patients will be discharged based on the clinical judgment of the investigator and standard of care at the study hospital. Patients who are discharged by Day 10 will have an End-of-study Visit 30 days after Day 10 or after the day of discharge (whichever is sooner), with a window of + 3 days, but not < 30 days.

Patients who discontinue study treatment prior to meeting the primary endpoint, GI2, will have an ET Visit and will be followed until 30 days after the day of discharge for safety. Patients who are withdrawn from the study will have an ET and an End-of-study Visit.

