8.2.5 Numerical Pain Rating Scale

The NPRS is an 11-point numerical scale on which patients will rate their pain on a scale of 0 (no pain at all) to 10 (worst possible pain) over the past 24 hours (see [Appendix 8](#)).

The scale is a reliable instrument for assessing pain intensity [6]. Pain will be assessed once daily in the morning at approximately the same time of day at the time points specified in the SoA, and the rating will be recorded in the eCRF ([Section 1.3](#)).

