#### **10.6 Pain Intensity as Assessed on Numerical Pain Rating Scale**

Values will be summarized using statistics for continuous variables for all available days. In addition, from Day 2 onwards the change from baseline will be summarized using statistics for continuous variables.

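### The named pain endpoint is change from a Day 1 score taken after dosing has begun, so any drug effect on pain already present on Day 1 drops out of it

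*SAP*

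**What the plan says.** Protocol Tables 1-1 and 3-1 list, under the objective of comparing the safety of three doses with placebo, "Change from baseline in pain intensity, as assessed on a Numerical Pain Rating Scale (NPRS").

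Both documents place the NPRS baseline on the first postoperative morning. Footnote l to the Schedule of Activities (SoA) says "baseline is defined as the pain assessment on the morning of Day 1", and SAP 6.5.2 says "The baseline value for NPRS will be the value as assessed on the morning of Day 1". For everything else SAP 6.5.2 uses a pre-treatment value: "Baseline except for the Numerical Pain Rating Scale (NPRS) will be defined as the last value obtained before randomization".

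On dosing, SoA footnote p and Protocol 4.1 put the first dose before surgery on Day 0. Protocol 4.1 adds that "the second dose will be administered postoperatively the evening of the operative day". SAP 8.1 allows that this second dose may not be taken, depending on when surgery is done.

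On the instrument, Protocol 8.2.5 has patients "rate their pain on a scale of 0 (no pain at all) to 10 (worst possible pain) over the past 24 hours", and the form in Appendix 8 asks about pain at the operation site.

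On analysis, SAP 10.6 summarises NPRS values for all available days and then adds that "from Day 2 onwards the change from baseline will be summarized using statistics for continuous variables". Protocol 9.4.6 plans summary statistics for NPRS at all time points. It mentions change from baseline only for laboratory tests and vital signs.

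**The concern.** A baseline used to compute change should not itself be affected by treatment. This one can be. It rates pain over a period in which patients had already received randomised study drug. If naldemedine alters pain from the first dose, the Day 1 score already carries that effect, and subtracting it removes the effect from every later change score.

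Pain matters for this drug and population. Naldemedine is an opioid antagonist, and Protocol 5.1 requires that opioids be the planned primary postoperative analgesia. Protocol 2.3 states that risks in this population are not known. Protocol 4.3 chose the lowest dose because it is estimated to give close to the target plasma concentration 12 hours after administration, so drug activity before the Day 1 rating is part of the design. If any loss of analgesia began early, a reader who looked only at the named endpoint could see no difference, or an apparent improvement, while pain was worse on drug.

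**Working it through.** The documents give no NPRS effect size, power or sample-size figure, so there is no stated figure to reproduce. The check is a dose count followed by an identity.

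**1. Doses before the baseline rating**

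- Scheduled: 2 (Day 0 before surgery, Day 0 evening).
- If the evening dose is not taken (SAP 8.1): 1.
- If the Day 1 morning dose is given before the rating: up to 3. SoA footnote l says only that the rating is made in the morning, so the order is not fixed.

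In every case at least one dose comes first.

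**2. What the change score estimates**

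Let d_1 and d_X be the true naldemedine-minus-placebo differences in mean NPRS on Day 1 and Day X (positive means more pain on drug). Then:

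expected arm difference in change = (drug X − drug 1) − (placebo X − placebo 1) = d_X − d_1.

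**3. Illustrative values**

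The shifts are assumed, in NPRS points. The last column is a simulation check with 200,000 patients per arm, assuming SD 2.5 and within-patient correlation 0.5; neither assumption affects the expected difference.

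| Pattern | d_1 | d_X (raw Day X difference) | d_X − d_1 | Simulated change difference |
|---|---|---|---|---|
| Constant worsening | 1.0 | 1.0 | 0.0 | 0.0 |
| Growing worsening | 0.5 | 1.0 | 0.5 | 0.5 |
| Early, fading | 1.5 | 0.5 | −1.0 | −1.01 |
| Early, gone by Day X | 1.5 | 0 | −1.5 | −1.49 |
| Starts after Day 1 | 0 | 1.0 | 1.0 | 0.99 |

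Only the last pattern is reported at its true size.

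**4. Where fading could arise**

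Protocol 4.1 ends dosing when GI2 is met or the discharge order is written. The SoA and Appendix 8 collect NPRS through the End-of-study Visit, about 30 days after discharge or Day 10. If a drug effect has gone by then, d_X = 0 and the change score shows −d_1: an early worsening appears as an improvement of the same size.

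**5. Precision of raw score against change**

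With equal variance σ² on both days and correlation ρ, the change score has variance 2σ²(1 − ρ). This is below σ² only if ρ > 0.5. The raw score therefore loses precision only in that case.

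**6. What a daily confidence interval would resolve**

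The 95% half-width for one dose minus placebo is about 1.96 × SD × √(2/n). Taking the plan's 44 and 85 per group and an assumed SD of 2.5:

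- n = 44: 1.96 × 2.5 × √(2/44) = 1.04 points.
- n = 85: 1.96 × 2.5 × √(2/85) = 0.75 points.

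For an SD of 2 to 3 the ranges are 0.84 to 1.25 and 0.60 to 0.90.

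**The case against.** The best defence is that the plan already shows the data needed. SAP 10.6 puts raw NPRS values first, for all available days including Day 1, and SAP 6.1 presents tables by treatment group. Protocol 9.4.6 describes its NPRS analysis as summary statistics at all time points, without mentioning change. Opioid dose in morphine milligram equivalents (MME) is a separate safety endpoint summarised daily (SAP 10.8), and the Clinical Opiate Withdrawal Scale (COWS) is summarised daily (SAP 10.7). None of these is measured from the Day 1 pain score. NPRS drives no test, threshold or stopping rule. All of this stands, and it limits the point: a reader might infer that an early effect on pain would vanish from the trial's results, and the documents do not support that. It would vanish from the named endpoint only. No between-arm NPRS difference or interval is planned, however, so the raw tables leave that comparison to the reader.

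A second defence is that the exception is deliberate. Pain at the operation site has no like-for-like value before the operation, so a preoperative rating would not serve. That is fair, and the two documents agree with each other. But it argues against using any change score here rather than for a baseline taken on treatment.

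Third, the drug is described as peripherally acting, and nothing in the documents shows that it reverses analgesia. A reader might take the worked values as a prediction of harm; they only show how the endpoint would behave.

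Fourth, it is tempting to say that randomisation makes raw scores comparable on every day. That is secure for Day 1 and weaker afterwards. SAP 6.4 uses observed cases without imputation, and if naldemedine speeds recovery, discharge may select who is still assessed on later inpatient days. Raw scores do not cure this, so the number assessed has to be shown.

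**Conclusion.** The point holds, within limits. The pain endpoint named in the protocol cannot show a drug effect already present in the Day 1 rating. All of d_1 is subtracted: a constant effect shows as zero, a fading one as a benefit, and one that starts later is kept in full. This follows from the definitions and needs no assumption about SD or correlation. Whether it matters in practice depends on an early effect on pain, for which the documents give neither evidence nor a size.

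The consequence is a safety endpoint that could mislead, not a hidden safety signal, because raw NPRS, MME and COWS summaries are also planned. No power or alpha figure changes. The correction is worth making because the comparison it asks for uses data already collected.

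**What to change.** - **Endpoint.** In Protocol Tables 1-1 and 3-1, SoA footnote l, and SAP 6.5.2 and 10.6, make the NPRS score by postoperative day the pain endpoint, with Day 1 as the first post-dose outcome and no longer a baseline.
- **Analysis.** In SAP 10.6, show each naldemedine dose minus placebo by day with a 95% CI, next to daily MME. Give the number of patients assessed in each arm each day, and note that later days are observed cases and may be selected by discharge.
- **Change score.** Keep change from Day 1 only as a descriptive table labelled as change from a post-dose value.
- **Timing.** State how the Day 1 rating relates in time to that morning's dose, so that readers know how much treatment it follows.

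The cost is wording in two endpoint tables, one footnote and two SAP sections, plus one extra table. No new visit, assessment or patient is needed. The downside is lower precision than a change score if the within-patient correlation exceeds 0.5.

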## 7. DEMOGRAPHIC AND OTHER BASELINE CHARACTERISTICS

### 7.1 Patient Disposition

The number of patients who failed the Screening Period (ie, screen failure) and its proportion to enrolled patients will be summarized along with the reason for not being randomized to treatment.

A summary table will be produced detailing the number of subjects randomized, the number of patients who completed the study, and the number of patients who prematurely discontinued from the study. In addition, the reason for discontinuation from the study will be summarized.

The number and proportion of patients in each analysis population to the randomized population will be summarized, as well as the reasons for exclusion from the mITT Population, the PPS, the Safety Analysis Population, PK-C and PK-P Populations.

### 7.2 Demographic and Baseline Characteristics

Demographic data and baseline characteristics shown in **Error! Reference source not found.** will be summarized descriptively as described in Section 6.1 for the mITT Population and the Safety Analysis Population. Prior surgeries can be any abdominal surgery except: gastrectomy, gastric bypass, gastric sleeve, lap banding, pancreatic resection, hepatectomy, intestinal transplant. Prior surgeries will be identified and finalized by the Shionogi Medical Monitor prior to database lock and unblinding. The categories used to summarize these data are shown in Table 7.

**Table 2 Demographic and Baseline Characteristics**

Continuous variable	• Age
Categorical variables	

• Sex

• Surgical procedure

• Fertility status for females

• Race

• Ethnicity

• Elements of the enhanced recovery protocol

• Prior surgery

Medical histories will be summarized by treatment group for the mITT Population. The reported medical history terms will be coded using Medical Dictionary for Regulatory Activities (MedDRA) Version 23.0.

## 8. STUDY CONDUCT

### 8.1 Treatment Exposure and Compliance

For the mITT Population and the Safety Analysis Population, the duration of treatment exposure and treatment compliance rate will be summarized descriptively by treatment group. The categories used in the summary of frequency counts (if applicable) are shown in Table 6.

The duration of treatment exposure will be defined as the dosing period during which a patient took the study drug:

$$(\text{final dose date}) - (\text{initial dose date}) + 1 \text{ [day]}$$

The treatment compliance rate will be defined as:

$$\frac{(\text{total number of tablets that patients actually took during duration of treatment exposure})}{(\text{total number of tablets that patients should have taken during duration of treatment exposure})} \times 100 \text{ [%]}$$

A dose will be considered one tablet. Patients will receive the study drug twice daily through Day 10; a total of two tablets per day will be administered. However, depending on the time surgery is done, patients may not take study drug after surgery on Day 0, which means the number of tablets can be one on Day 0.

